### Confocal laser endomicroscopy, CLE:

- A probe-based endoscopic technique to study intestinal food reactions after iv injection of fluorescein.
- Disruption of the small intestinal barrier in duodenum upon exposure to food antigens (soy, wheat, egg, gluten, milk, and control) can be determined.
- Can detect and quantify changes in intestinal tissues and cells, including increases in intraepithelial lymphocytes and fluid extravasation through epithelial leaks in real time.

### Visceral sensitivity:

- Rectal barostat sensitivity measurement: With the rectal barostat we can measure the rectal sensitivity. A balloon is inserted and inflated in the rectum in a controlled setting. The patient indicates when defined sensory thresholds are reached (first feeling of the balloon, urge to empty bowel, discomfort or pain). When the patient indicates discomfort or pain, or another reason to stop, the balloon inflation will be stopped.

### Sigmoidoscopy:

- Flexible sigmoidoscopy without bowel preparation, to interfere as little as possible with the normal gut microenvironment; fresh biopsies for specific analyses and biopsies stored for subsequent analyses.

### Biological samples:

- Blood – and plasma samples: Fasting blood samples are taken for routine blood tests (exclusion of organic diseases) and to determine the metabolic profile and genetic and immunological markers of relevance to intestinal function and nerve function. Serum samples will be analyzed with nuclear magnetic resonance (NMR) for metabolomic profile and microbial composition.
- Fecal – and urine sample: We will characterize the composition and function of the metabolome in detail via 16S analysis, metagenomics, transcriptomics, metabolomics, cell culture and cell count. Urine and fecal samples will also be analyzed with nuclear magnetic resonance (NMR) for metabolomic profile and microbial composition.
- Biopsies from the stomach or the colon (location based on the performed endoscopic examination): We will conduct a detailed analysis of immune cells, proteins, nerve cells, and intestinal bacteria which will allow detailed mapping of intestinal function with respect to nerve, immune and barrier function.

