## Aim

To define local immune responses in the GI tract to food antigens in IBS patients with and without *Brachyspira* infection using advanced imaging.

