## Methods

### Subjects

All patients will be carefully characterized at baseline including detailed clinical phenotyping, allergy testing, nutrient intake, detailed information about adverse food reactions, collection of blood and fecal samples, and identification of *Brachyspira* in colonic biopsies. Before and after the endoscopic food challenge, biopsies will be taken. These will be analyzed with a particular focus on the mucosal immune response (e.g. tryptase activity, as a measure of mast cell degranulation; immunohistochemistry to determine IgE/mast cells and other immune cells; mucosal structure, eosinophils, and intraepithelial lymphocytes with Hematoxylin and Eosin histology). Baseline characteristics (e.g. clinical and nutritional profile, gut microbiota composition and function, *Brachyspira* infection, immune activation) associated with a positive food challenge test, i.e. with an intestinal allergy-like reaction, will be determined.

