### **Visit 3 – CLE or COLAP test – 5 hours**

1. Blood test, microbiota, immunological markers and metabolites. The subjects come fasting (8 hours: CLE , or according to laxatives protocol: COLAP) to our lab. The researcher will freeze fecal (10g) samples in minus 80 degrees for later analyses.

2. A) CLE. The researcher and gastroenterologist explain the procedure. Check if patient complied with dietary guidelines. The subjects undergo the CLE. Biopsies will be frozen. B) COLAP. The researcher and gastroenterologist explain the procedure. Check if patient complied with bowel preparation and dietary guidelines. The subjects undergo the COLAP. Biopsies will be frozen.

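### The only biopsy site the protocol offers for CLE is the stomach, but the CLE food challenge is in the duodenum

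*Protocol*

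**What the plan says.** The Biological samples section gives two biopsy sites, chosen by procedure: "Biopsies from the stomach or the colon (location based on the performed endoscopic examination"). It gives the purpose as "detailed mapping of intestinal function with respect to nerve, immune and barrier function".

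The Confocal laser endomicroscopy section describes what the CLE challenge shows: "Disruption of the small intestinal barrier in duodenum upon exposure to food antigens".

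The Subjects section sets the timing of the challenge biopsies, "Before and after the endoscopic food challenge, biopsies will be taken", and their use: "These will be analyzed with a particular focus on the mucosal immune response". The first measure it names is "tryptase activity, as a measure of mast cell degranulation". It also names immunohistochemistry for IgE and mast cells, and histology that includes eosinophils and intraepithelial lymphocytes.

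For the CLE arm of Visit 3 the protocol says: "The subjects undergo the CLE. Biopsies will be frozen".

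The Aim is "To define local immune responses in the GI tract to food antigens", in IBS patients with and without *Brachyspira* infection.

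**The concern.** A before-and-after comparison of biopsies measures a local reaction to a food only if the tissue comes from the mucosa that met the food. The one section that assigns biopsy sites across the endoscopic examinations leaves the stomach as the only site available for CLE, while the CLE section puts the challenge in the duodenum.

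At stake is the biopsy part of the CLE challenge. The CLE section names barrier disruption, intraepithelial lymphocytes and fluid leakage as changes it can detect. It does not name tryptase activity, IgE/mast cells or eosinophils, so in CLE patients these three rest on the biopsies as the protocol is written. If the tissue is gastric, a change in them, or the absence of one, does not address the Aim. Tissue taken from the wrong site cannot be corrected at analysis.

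**Working it through.** No arithmetic applies beyond counting, so the check sets the sections side by side.

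**Step 1: which procedure can each listed site belong to?**

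| Procedure | Where the protocol places it | Site under Biological samples that fits |
|---|---|---|
| Sigmoidoscopy (Sigmoidoscopy; Visit 2) | Lower bowel | Colon |
| COLAP (COLAP; Visit 3) | Sigmoid mucosa | Colon |
| CLE (CLE; Visit 3) | Duodenum | Neither |

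CLE is the only upper gastrointestinal procedure described. The stomach can therefore refer only to CLE, and it is not where the food is applied or the reaction read.

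**Step 2: does another section supply the site?** Six sections mention biopsies: Subjects, COLAP, Sigmoidoscopy, Biological samples, Visit 2 and Visit 3. The COLAP, Sigmoidoscopy and Visit 2 sections have no reason to name a CLE site. That leaves 6 − 3 = 3 sections that bear on CLE biopsies:

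| Section | Site given for CLE biopsies |
|---|---|
| Subjects | None for the before-and-after biopsies (colonic tissue is named only for identifying *Brachyspira*) |
| Biological samples | Stomach, by elimination |
| Visit 3 | None |

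One of the 3 gives an organ that can apply to CLE, and it is the stomach. None of the 3 names the duodenum. Subjects and Visit 3 do not exclude it either. In the whole protocol the duodenum is named only in the CLE section and the stomach only under Biological samples.

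**Step 3: does the parenthesis about the examination performed resolve it?** It selects between the two organs listed and does not add a third.

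**Step 4: which measures are concerned?** Of the biopsy measures named under Subjects, tryptase activity, IgE/mast cells and eosinophils are not among the changes the CLE section says it detects. That makes at least 3 measures that depend on the biopsy site. Intraepithelial lymphocytes are left out of this count because the CLE section claims to detect their increase directly.

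**Step 5: how far does it reach?** Visit 3 offers CLE or COLAP, so 1 of the 2 alternative challenges is concerned. The protocol does not state how many patients have each.

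**The case against.** The strongest reply is that this is one loose word in a general sample list. The Biological samples entry does not say that its list is exhaustive, and it mentions neither CLE nor before-and-after sampling. It lets the site follow the examination, and its stated purpose is to map intestinal function, which gastric tissue does not fit. The Aim, the Subjects section and the CLE section all point towards the challenged mucosa. On the whole document, *stomach* may simply mean the upper gut as opposed to the lower. No section states outright that CLE biopsies are gastric. The counts above show where sites are named and measure no effect on any result.

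Much of this stands. The benign reading is plausible, the harm depends on the literal reading, and the point should not be presented as evidence that the CLE biopsy results are invalid.

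It does not remove the conflict. The word has to refer to CLE, because no other procedure reaches the upper gut. The mismatch with the entry's own purpose shows that something in it is wrong, but does not tell the endoscopist where to sample. If the entry were not meant to cover the challenge biopsies at all, those taken around CLE would have no stated site, and the same clarification would be needed. Nor is this a matter for an analysis plan: the tissue site is procedural and belongs in the protocol.

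**Conclusion.** The concern holds: the biopsy site is wrong as written. The only site the protocol makes available for CLE biopsies conflicts with where it places the CLE challenge, and with an Aim that concerns local responses to food.

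The severity is minor and the confidence medium. The point touches at least three tissue measures in patients who have CLE. It leaves alone the real-time CLE read-out, the decision on who proceeds to visits 4 to 6 (which rests on a positive CLE or COLAP), and everything in COLAP patients. No percentage of patients can be given, because the protocol does not state the split between CLE and COLAP.

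The conclusion rests on two readings of the text: that the Biological samples entry covers the biopsies taken at the CLE visit, since nothing limits it to other samples, and that CLE is the only upper gastrointestinal procedure, since no other is described. Whether *stomach* was meant literally is not settled by the document.

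**What to change.** Reconcile the Subjects, CLE, Biological samples and Visit 3 sections:

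- State under Subjects and Visit 3 that the before-and-after CLE biopsies come from the segment exposed to the food, which the CLE section gives as the duodenum.
- Replace *stomach* in the Biological samples entry so that it agrees.
- If gastric tissue is wanted for another purpose, list it as a separate sample and say that it is not the challenge read-out.

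If the word was loose, this costs a wording change. If gastric sampling was really planned for the challenge read-out, it costs at most a change of sampling site within an endoscopy already planned, with no extra procedure.

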## Study visits

### **Visit 1 – screening visit – 2 hours**

1. Screening. The subjects come fasting (8 hours) to our lab and the researcher obtains informed consent, confirms the IBS diagnosis and study criteria. Clinical routine blood tests for diagnostic purposes (blood cell count, liver, kidney, thyroid gland status, electrolytes, fasting glucose, C-reactive protein, transglutaminase (gluten) antibodies, and faecal calprotectin. The subjects fill in the baseline questionnaires. Height and weight are measured.

2. Rectal barostat. The researcher explains the rectal barostat procedure and the subjects undergo the rectal barostat. Thereafter, they will obtain information about the screening period including questionnaires, tubes for fecal and urine samples. Visit 2 and 3 will be planned.

### **Period before visit 2 – 14 days**

The subjects register their dietary intake (food diary) for 4 days before visit 2. GI symptoms and bowel habits (BSFS) are registered during 14 days (GI diary), as well as IBS symptoms according to 2 questionnaires (IBS-SSS and GSRS-IBS) during the preceding week.

**Allergologist:** Through visits to the allergology clinic, (food) allergies will be excluded according to usual clinical routine (blood tests and prick tests)

### **Visit 2 – Sigmoidoscopy – 2 hours**

1. Blood test, microbiota, immunological markers and metabolites. The subjects come fasting (8 hours) to our lab, where a nurse will take fasting blood samples (20 ml). The researcher will freeze fecal (10g), urine (3ml) and serum (5ml) samples in minus 80 degrees for later analyses. Pregnancy test (urine) is taken.

2. Questionnaires. The researcher checks the filled in questionnaires (screening period) and the subjects fill in the web-based questionnaires.

3. Sigmoidoscopy. The researcher and gastroenterologist explain the procedure. No bowel preparation, fresh biopsies will be taken for specific analyses and biopsies will be stored (a.o. -80 degrees Celsius) for subsequent analyses.

### **Visit 3 – CLE or COLAP test – 5 hours**

1. Blood test, microbiota, immunological markers and metabolites. The subjects come fasting (8 hours: CLE , or according to laxatives protocol: COLAP) to our lab. The researcher will freeze fecal (10g) samples in minus 80 degrees for later analyses.

2. A) CLE. The researcher and gastroenterologist explain the procedure. Check if patient complied with dietary guidelines. The subjects undergo the CLE. Biopsies will be frozen. B) COLAP. The researcher and gastroenterologist explain the procedure. Check if patient complied with bowel preparation and dietary guidelines. The subjects undergo the COLAP. Biopsies will be frozen.

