## Measurements/tests

### Colonoscopic allergen provocation test, COLAP:

- A local allergen provocation test, where dietary antigens (soy, wheat, egg, gluten and milk), with saline and histamine as negative and positive controls, respectively are injected in the sigmoid mucosa (similar to skin prick test used for clinical allergy testing).
- The intestinal reaction is determined visually (“wheal and flare reaction”), and biopsies are taken to characterize the immune response.
- Bowel preparation before the investigation follows the normal clinical routine for colonoscopy, and i.v. sedatives and opioids are given during the investigation according to clinical routines at the endoscopy unit

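### The only pregnancy test is at Visit 2; the drug exposures come at Visit 3, after an unstated interval and with no repeat test listed

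*Protocol*

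**What the plan says.** - **Exclusion criteria.** Pregnancy and lactation exclude a woman, judged at the time of inclusion. Women of fertile age are asked to use safe contraception.
- **Visit 1.** The routine blood tests are itemised and include no pregnancy test. On scheduling, the text says only "Visit 2 and 3 will be planned".
- **Visit 2.** "Pregnancy test (urine) is taken" is the only pregnancy test in the document. The procedure at this visit is described as "Flexible sigmoidoscopy without bowel preparation, to interfere as little as possible with the normal gut microenvironment". Neither the Sigmoidoscopy section nor the Visit 2 section lists a sedative, contrast agent or injection.
- **Visit 3, CLE.** The technique is "A probe-based endoscopic technique to study intestinal food reactions after iv injection of fluorescein". The check listed before it is "Check if patient complied with dietary guidelines".
- **Visit 3, COLAP.** Dietary antigens, "with saline and histamine as negative and positive controls, respectively are injected in the sigmoid mucosa", and "i.v. sedatives and opioids are given during the investigation according to clinical routines at the endoscopy unit". The check listed before it is "Check if patient complied with bowel preparation and dietary guidelines".

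**The concern.** The protocol treats pregnancy as a reason not to take part and orders a test to detect it. It then places that test at the endoscopy with the least listed exposure, not at the visit where fluorescein, or histamine with sedatives and opioids, is given. A urine test shows status on the day it is taken, and nothing limits the time from that day to Visit 3. A woman who becomes pregnant between the two visits could undergo either Visit 3 procedure without any check that the protocol lists. The stake is participant safety in a research procedure; an exposure in an unrecognised pregnancy cannot be undone afterwards.

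**Working it through.** There is no planned figure to reproduce. The check sets the visit schedule against the procedure descriptions, then illustrates the size on assumed values.

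**Exposure against pregnancy check**

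| Visit | Procedure | Listed drug or injection | Listed pregnancy test |
|---|---|---|---|
| 1 | Screening, rectal barostat | none | none |
| 2 | Sigmoidoscopy | none | urine test |
| 3 | CLE | intravenous fluorescein | none |
| 3 | COLAP | antigens, saline and histamine into the mucosa; intravenous sedatives and opioids | none |

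The sample named for freezing at Visit 3 is faeces. Urine is named at Visit 2 but not at Visit 3, so no listed sample would prompt a urine test there.

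**Timing.** Three intervals are fixed: 14 days before Visit 2, 4 weeks from Visit 4 to Visit 5, and 4 weeks from Visit 5 to Visit 6. The interval from Visit 2 to Visit 3 has no stated value and no maximum, and it cannot be derived from the others.

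**Consistency with the exclusion criterion.** The criterion concerns status at inclusion and can be read as completed by the Visit 2 test. The schedule therefore does not contradict it. What remains uncovered is the time after that test.

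**Illustrative size.** Let r be the rate of new pregnancies per woman-year and w the gap in weeks. Both are assumptions; the protocol gives neither, nor the number of women of fertile age.

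New pregnancies per 1,000 women = 1000 × (1 − exp(−r × w / 52))

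| r per woman-year | w (weeks) | r × w / 52 | Per 1,000 women |
|---|---|---|---|
| 0.01 | 1 | 0.00019 | 0.19 |
| 0.01 | 4 | 0.00077 | 0.77 |
| 0.10 | 4 | 0.00769 | 7.66 |
| 0.10 | 12 | 0.02308 | 22.81 |

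The full range is about 0.2 to 23 per 1,000, and at 4 weeks about 0.8 to 8 per 1,000. For rates this low the figure grows almost in proportion to w, the quantity the protocol leaves open.

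**The case against.** The strongest reply is that pregnancy is already handled by three measures (exclusion, requested contraception and a test before the first endoscopy), so only a small residual risk is left. That is fair as to rarity. But contraception is requested with no verification listed, and the other two measures look no further than Visit 2.

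Second, the Visit 3 section is a summary. Its first item has blood tests in its title but describes no blood draw, and the section does not name the drugs given. Its silence is therefore imperfect evidence of what will be done. This stands as a caution. Even so, the section does state a check before each procedure, and pregnancy is in neither.

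Third, COLAP sedation follows endoscopy-unit routine, which may include a pregnancy check. This is possible, and it makes the COLAP half of the point weaker. The protocol does not say so, however, and cites no such routine for fluorescein in CLE. Nor was routine relied on at Visit 2, where a test is written in.

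Fourth, Visits 2 and 3 are planned together and may fall within days of each other. If so, the gap is minor, but nothing requires it.

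Fifth, participant consent pages are not available here and may contain pregnancy instructions. Such instructions would help, but they would not put a test into the Visit 3 schedule.

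Finally, the protocol states no fetal risk for any of these agents, and the rates above are assumed. Both are true. The point makes no claim about the degree of harm, and the rates only illustrate scale.

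**Conclusion.** The concern holds. The single pregnancy test sits at the visit with the least listed exposure. The visit with the drug exposures has no listed test, and the time between the two has no limit. It is a safeguard placed badly, not an internal contradiction, and it does not touch the statistical analysis.

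The event is rare: about 0.2 to 23 per 1,000 women of fertile age under the assumed rates and intervals, with no expected count possible because the protocol gives no number of such women. The point is firmest for CLE. For COLAP it depends on whether unit routine already includes a check. The change should be made, because it is cheap and closes a real gap; the study is not invalidated without it. Confidence is medium, because local practice cannot be seen from the document.

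**What to change.** Add one line to the Visit 3 checks, under both CLE and COLAP:

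> Women of fertile age: same-day negative urine pregnancy test before the procedure; if positive, the procedure is not done.

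Optionally, state that eligibility is final only after the Visit 2 test. A maximum interval from Visit 2 to Visit 3 would shorten the gap but, unlike a same-day test, would not close it.

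The cost is one line of protocol text, plus one urine sample and one inexpensive test per woman of fertile age at a visit she already attends. No extra visit, staff or invasive procedure is needed, and the analysis is unchanged.

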**Visit 4-6: only if COLAP or CLE were positive for 1 or more food items.**

### **Visit 4**

Questionnaires (IBS-SSS, GSRS-IBS, HAD, PHQ-15). Instructions and advice from the dietician which food item(s) to exclude from the diet, based on CLE or COLAP. Period of exclusion: 4 weeks.

### **Visit 5 (digital, 4 weeks after visit 4)**

Questionnaires (IBS-SSS, GSRS-IBS, HAD, PHQ-15). Instruction to re-introduce the CLE or COLAP positive food item(s) for 4 weeks.

***Visit 6 (digital, 4 weeks after visit 5)***

Questionnaires (IBS-SSS, GSRS-IBS, HAD, PHQ-15).
